5.2. Preparation/Handling/Storage/Accountability

The investigational products are intended for the detection of MTB in patient samples as well as the detection of MTB mutations associated with resistance to Rifampicin. The investigational products will be strictly accounted for, including receipt and inventory, storage, use during the trial, and return or disposal, as detailed in the Manual of Procedures provided by FIND.

Acquisition: Procurement of the investigational products will be done through FIND, which will coordinate shipments from the manufacturer. It is the responsibility of each trial site to maintain an updated inventory of the trial materials and to inform FIND immediately if additional materials are required.

Storage: Procedures for product storage and disposal will be described in the Manual of Procedures. Briefly, investigational products will be checked for quality at the time of receipt at the site. Investigational products will be stored according to the manufacturer's instructions; expired or unused investigational products will be destroyed with documentation. The investigator or designee must confirm appropriate temperature conditions have been maintained during transit for all devices, reagents and samples received and any discrepancies are reported and resolved before use of the trial intervention.

Test handling and performance: Testing using the investigational products will be performed according to the manufacturer's instructions outlined within the Manual of Procedures. Only participants enrolled in the trial may have samples evaluated using the medical devices described herein, and only authorized site staff may process samples and perform the diagnostic test. All trial medical devices, reagents and samples must be stored in a secure, environmentally controlled, and monitored (manual or automated) area in accordance with the labelled storage conditions with access limited to the investigator and authorized site staff.

The investigator, institution, or the head of the medical institution (where applicable) is responsible for trial intervention accountability, reconciliation, and record maintenance (ie, receipt, reconciliation, and final disposition records).

Import permits: It is expected that most countries will require import permits for receiving the investigational materials. Local sites are responsible for making import permit applications in a timely manner.

Quality control check for incoming shipments: Upon arrival of each new shipment of assays, the sites will conduct and document an incoming quality check following the Manual of Procedures. New lots may only be used after this quality check is successfully passed.

Local procurement: Sites are responsible for assessing their needs and procuring any supplies, reagents and kits needed for the trial that are locally available in order to include these costs in the trial budget.

5.3. Minimization of Error and Bias

5.3.1. Patient selection

Spectrum bias will be avoided by enrolling a consecutive series of subjects and using a cross-sectional trial design. Enrolment will be based on clearly defined eligibility criteria, targeting patients suspected to have TB as defined by WHO12, thus representing future target populations. Descriptive statistics on patient characteristics and estimates of diagnostic accuracy stratified by site, smear and HIV status to further ensure the validity and generalizability of trial results will be provided.

5.3.2. Index test

The risk of review bias is minimal. Interpretation of results from the index tests does not require interpretation by the end-users and is based on pre-defined and automatically implemented thresholds. Further, results will become available and will be recorded before those of the reference standard (culture or DST). Where other rapid molecular assays are performed on the same sample, laboratory staff members will be instructed to record results independently of other test results.

5.3.3. Reference standard

Each participating laboratory will undergo an on-site laboratory evaluation to ensure standardized and high-quality performance of culture across sites (see also section Quality Assurance). Results from reference standard testing will be recorded blinded to index test results, eliminating the risk of review bias. Presence of MTB complex will be confirmed for all patients from a positive culture using MPT64 identification test and/or Line Probe Assay.

A reference standard of MTB culture (using two MGIT and two LJ cultures) will be used for TB detection. For RIF resistance detection a composite reference standard of phenotypic and genotypic RIF DST by sequencing will be used (as detailed in section Case definitions). This will allow for a high confidence in the interpretation of Truenat RIF resistant assay results. RIF sequencing will be done at a central laboratory for standardisation purposes (where possible).

5.3.4. Flow and timing

The planned patient and sample flow includes testing of three samples per patient with the index test and reference standard and there is thus little risk of disease progression bias. Manual mixing or splitting of decontaminated sample (pellet) together with random allocation of pellet aliquots (i.e. pipetting order) will also ensure that neither the index test nor the reference standard test are given an artificial advantage by virtue of being used on a higher quality sample.

5.3.5. Handling of indeterminate results

Samples for which the index test is indeterminate or cultures are contaminated will be excluded from the main accuracy analyses but reported separately. Results based on initial testing only as well as those obtained upon repeat-testing (for indeterminate results, where possible) will be presented.

5.3.6. Blinding Procedure

This is an open-label trial. The results of the Truenat MTB and RIF assays are generated automatically. Nevertheless, there is a potential bias of laboratory tests that are subject to operator's interpretation such as smear microscopy and LJ culture.

- Different operators will be assigned to Xpert MTB/RIF and smear microscopy. Similarly for MGIT and LJ culture.
- Technicians will be instructed to record results independently of other test results.

6. Discontinuation of Trial Intervention and Participant Discontinuation/Withdrawal

6.1. Participant Discontinuation/Withdrawal from the Trial

- A participant may be withdrawn at any time at the discretion of the investigator for safety, behavioural, compliance, or administrative reasons.
- Participants who withdraw will be referred to the appropriate local health service for TB evaluation and care. If positivity for MTB is confirmed (through sputum smear microscopy, mycobacterial cultures or Xpert MTB/RIF), results will be reported to appropriate local health authorities in accordance with local public health reporting regulations.

- If the participant withdraws consent for disclosure of future information, FIND may retain and continue to use any data collected before such a withdrawal of consent.
- If a participant withdraws from the trial, he/she may request destruction of any samples taken and not tested, and the investigator must document this in the site trial records.
- See Manual of Procedures for data to be collected at the time of trial discontinuation and follow-up.

6.2. Lost to Follow Up

A participant will be considered lost to follow-up if he or she repeatedly fails to return for scheduled visits and is unable to be contacted by the trial site.

The following actions must be taken if a participant fails to return to the clinic for a required trial visit:

- The site must attempt to contact the participant and reschedule the missed visit as soon as possible and counsel the participant on the importance of maintaining the assigned visit schedule and ascertain whether or not the participant wishes to and/or should continue in the trial.
- Before a participant is deemed lost to follow up, the investigator or designee must make every effort to regain contact with the participant. These contact attempts should be documented in the participant's medical record.
- Should the participant continue to be unreachable after 3 attempts at different time points, he/she will be considered to have withdrawn from the trial.

7. Trial Procedures

- Trial procedures and their timing are summarized in the SOA. Protocol waivers or exemptions are not allowed.
- Adherence to the trial design requirements, including those specified in the SOA, is essential and required for trial conduct.
- Eligibility criteria must be completed and reviewed to confirm that potential participants meet the requirements. The investigator will maintain a screening log to record details of all participants screened and to confirm eligibility or record reasons for screening failure, as applicable.
- Procedures conducted as part of the participant's routine clinical management (e.g. chest X-ray) and obtained before signing of the ICF may be utilized for screening or baseline purposes provided the procedures met the protocol-specified criteria and were performed within the time frame defined in the SOA.

7.1. Trial Workflow

Following initial screening, individuals will be referred to trial personnel for additional information and to review eligibility (if initial assessment was done by non-trial clinicians). If appropriate, samples will be obtained following the informed consent process. Information on signs/symptoms (duration of cough, fever, haemoptysis, night sweats and weight loss) and TB history (previous TB episodes, dates of treatment, treatment outcome) will be obtained. Information on TB history will be critical given the potential for molecular tests to detect DNA from nonviable, non-intact bacilli in patients with recent history of TB¹⁰.

7.2. Efficacy Assessments

See section 10.4 Efficacy Analyses.

7.3. Safety Assessments

See Section 9, Safety and Incident Reporting.

7.4. Health Economics

The data collected may be used to conduct exploratory economic analyses and a specific study protocol will be prepared.

8. Specimen Collection, Handling, Transport and Storage

Participants will be asked to provide a total of four sputum samples at enrolment and over 2 days. The intent is for all samples to be collected before the participant starts any form of TB treatment, unless the participant is part of the Drug Resistant TB group.

Each specimen should be of 2 ml or greater in volume. On Day 1, each participant will be asked to submit two spot sputa (S1 and S2, approximately 30-60min apart) after enrolment. Participants will be given a labelled sputum pot and instructions for use, and instructed to collect a second sputum (S3) the next morning (Day 2) before going to the clinic. At the clinic participants will be asked to provide a third spot sputum (S4). In the event that a participant fails to return on Day 2, S3 and S4 may be collected a maximum of 7 days after enrolment, provided that no TB treatment has been initiated (the Case Detection group).

HIV testing will be offered to all participants as part of the trial procedures unless any one or more of the following are present:

- written results of a positive HIV antibody test;
- written results of a positive HIV viral load;
- documentation in the medical record of positive HIV status by a treating clinician;
- immediate/verifiable documentation of HIV negativity within the preceding one month.

HIV testing can be performed using any test method approved by local health authorities. Depending on the test method used, this test will require approximately 1 ml of saliva (rapid oral test), or up to approximately 5 ml of blood. Participants refusing to undergo HIV testing will not be excluded from the trial.

8.1. Reference Standard Test and Index Test Procedures

At each site, as per laboratory flow (Figure 2), standard diagnostic algorithms will be followed according to national guidelines and policies of each participating country. If national guidelines cannot be fulfilled using study-specific samples and test results, then an additional spot sputum should be collected.

Sites: All

[figure not shown]

Figure 2. Laboratory workflow

Study spot Sputum 1 (S1) will be collected on Day 1. Approximately 30-60 minutes later, a second spot sputum (S2) will be collected and sent directly to the reference laboratory.

Participants will be given a labelled sputum pot and instructions on how to use it to collect an early-morning sputum (S3), and asked to bring this back to the clinic the next day (Day 2), and provide another spot sputum (S4).

On Day 1, smear microscopy will be performed on Sputum S1 and S2 in the reference laboratory or, if required, in the microscopy centre. In the reference lab, S1 and S2 will be pooled together and homogenised using glass beads and a vortex. Homogenised sputa will be further split: 1.5ml will be used for analysis on raw sputa, and at least 2ml used for NALC-NaOH decontamination.

Briefly, DNA will be extracted independently from i) raw sputum and ii) decontaminated pellet, by the Trueprep Auto device and tested by both the Truenat MTB and the MTB Plus chips, both of which are read by the Truelab UnoDx real-time PCR analyser. All DNA samples testing positive by the MTB assay will be subsequently tested by the Truenat MTB-RIF Dx assay (reflex) which is also read by Truelab UnoDx analyser.

Xpert assays will be performed on the same raw and decontaminated samples.

MGIT and LJ culture will be performed on only on the decontaminated sample.

On Day 2, morning sputum S3 will be returned to the clinic in a labelled sputum pot and the participant will be asked to provide spot sputum S4. S3 will be sent to the reference laboratory and a second round of MGIT and LJ culture will be performed on decontaminated sample. As for S1 and S2, each positive culture will be identified for MTB complex using MPT64 identification test and/or Line Probe Assay. MGIT SIRE will be used to determine the phenotypic DST for RIF. All samples that exhibit RIF resistance, as determined by either phenotypic DST or Truenat RIF, will be sent for DNA sequencing to determine the mutations responsible for drug resistance. A subset of drug sensitive samples, of approximately matching sample size, will be randomly selected for sequencing, to act as a comparator sequence.

Spot sputum S4 will be processed in the microscopy centre: 500ul raw sputum will be used for DNA extraction by Trueprep Auto and MTB detection by the Truenat assays. Any MTB-positive samples will be subsequently tested by the Truenat MTB-RIF Dx assay (reflex).

The intended objective is to test the Truenat assay in the setting of use (i.e. microscopy centre). If the microscopy centre has an Xpert machine (or if the

microscopy centre and the reference lab are the same), then the Truenat assay need only be performed once along side Xpert (on Day 1).

All leftover pellet, eluate and culture isolates will be stored as per the Manual of Procedures for further testing in case of discordant results e.g. result of Truenat RIF differs from that of phenotypic DST or Xpert MTB/RIF.

Importantly, laboratory technicians performing smear microscopy will be blinded to the results of Truenat MTB assays and other conventional test results. Moreover, the results of the Truenat MTB assays and Truenat RIF will not be reported back to the clinic i.e. will not be used for patient management.

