1.2 Background

The Truenat MTB and MTB plus assays and the MTB-RIF Dx (Truenat RIF or RIF assay) assay (Molbio Diagnostics; Bangalore, India) utilize chip-based real-time micro PCR for detection of TB and rifampicin (RIF) resistance from DNA extracted from sputum samples in about 25 minutes⁷. Briefly, automated DNA extraction is performed using the Trueprep Auto sample prep device (Figure 1). The extracted DNA is then added onto the Truenat MTB (or MTB plus) chip which is pre-loaded with stabilized reagents. Automatic amplification and analysis is then done using a handheld battery-operated device, the Truelab UnoDx real time PCR analyser. If the Truenat MTB (or MTB plus) chip is positive- and dependent on the diagnostic algorithm being employed- the user can then take another aliquot of extracted DNA and add it onto a separate Truenat MTB-RIF Dx chip to detect the presence of selected mutations associated with rifampicin resistance. A pilot trial conducted in India of the Truenat MTB assay found the assay to achieve 91% sensitivity and 100% specificity against a composite reference standard, including 99% sensitivity for smear-positive, culture-positive samples and 76% sensitivity for smear-negative, culture-positive samples⁸. However, further evidence of the performance and operational characteristics of the Truenat MTB assay, as well as the Truenat MTB plus (alternative version including an additional gene target

for TB detection) and RIF Reflex assay, is needed prior to recommending the clinical use of the assays.

Figure 1. Truenat MTB assays steps. A mixture of raw sputum and liquefaction buffer is directly loaded onto the Trueprep Auto chip interface, which extracts MTB DNA in 25 minutes. The extracted DNA is transferred to the Truenat MTB (or Truenat MTB Plus) chip and then onto the Truelab UnoDx PCR machine, which detects the presence of MTB DNA, and provides an automated result as either MTB-detected, MTB not detected or indeterminate result. For MTB positive results, another aliquot of the same DNA extracted is then transferred (reflex) to the Truenat MTB-RIF Dx chip.

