8.3. Other Trial Procedures

8.3.1. Assessment of patient important outcomes

The following will be assessed as patient important outcomes using the Truenat MTB assays and RIF assay compared to routine tests

- Time to detection of TB and susceptibility to RIF.
- Yield over smear microscopy and Xpert MTB/RIF.
- Upfront diagnosis of RIF (reflex on all Truenat MTB or MTB Plus positive versus current standard of smear-positive reflexed to Xpert MTB/RIF based on risk factors).

See Patient important outcomes under Statistical analysis plan.

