10.1. Statistical Hypotheses

Primary endpoint 1.1 is to assess the diagnostic accuracy of the Truenat MTB assays for MTB detection among individuals undergoing evaluation for pulmonary TB, overall and per sample, separately for smear-positive and smear-negative TB samples using a culture reference standard.

Primary endpoint 1.2 will estimate diagnostic accuracy of the Truenat RIF assay for RIF resistance detection among individuals undergoing evaluation for pulmonary TB and DR TB, using a reference standard of phenotypic/genotypic DST i.e. MGIT SIRE and sequencing for RIF resistance.

Secondary endpoints will compare the diagnostic accuracy of the Truenat MTB assays and RIF assay to that of Xpert MTB/RIF, using a reference standard of culture for TB diagnosis and MGIT SIRE and sequencing for detection of RIF

resistance. Additionally, the trial will assess patient important outcomes, including: i) time to detection of TB and RIF resistance, ii) yield over smear microscopy and Xpert MTB/RIF and iii) upfront diagnosis of RIF (reflex testing on all Truenat MTB or MTB Plus positive versus current standard of smear-positive reflexed to Xpert MTB/RIF based on risk factors).

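### As written, the Day-1 RIF reflex trigger in section 8.1 omits DNA positive on MTB Plus alone, which the upfront-RIF outcome counts

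*Protocol*

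**What the plan says.** Section 8.1 of the protocol takes two DNA extracts from the pooled Day-1 sputum, one from raw sputum and one from the decontaminated pellet. Each is "tested by both the Truenat MTB and the MTB Plus chips". The next sentence gives the reflex rule: "All DNA samples testing positive by the MTB assay will be subsequently tested by the Truenat MTB-RIF Dx assay (reflex". MTB Plus is not named in it.

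For the Day-2 spot sputum (S4), the same section describes "MTB detection by the Truenat assays" at the microscopy centre, followed by a rule in other words: "Any MTB-positive samples will be subsequently tested by the Truenat MTB-RIF Dx assay (reflex". Where the microscopy centre has Xpert, or is itself the reference laboratory, "then the Truenat assay need only be performed once along side Xpert (on Day 1", so S4 need not be tested there.

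The outcome is defined more widely. Section 8.3.1 lists "Upfront diagnosis of RIF (reflex on all Truenat MTB or MTB Plus positive", against the current standard of smear-positive cases reflexed to Xpert. Section 10.1 repeats it as a secondary endpoint: "upfront diagnosis of RIF (reflex testing on all Truenat MTB or MTB Plus positive". The product description in section 1.2 also lets either chip lead to the RIF chip: "If the Truenat MTB (or MTB plus) chip is positive".

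**The concern.** A laboratory that follows section 8.1 to the letter would not run the RIF chip on a Day-1 extract that is MTB Plus positive and MTB negative. The outcome in sections 8.3.1 and 10.1 nevertheless counts that sample. MTB Plus carries an additional gene target (section 1.2), so such samples are plausible, and the sample size in section 10.2 rests on the expected sensitivity of MTB Plus.

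Three results would be incomplete for this subset:

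- **RIF-resistant cases detected (section 10.5.3).** For an algorithm that starts with MTB Plus, leaving the samples out can only lower this count or leave it unchanged.
- **RIF indeterminate rate (section 10.5.5).** It would go unobserved in samples that are probably low in bacilli.
- **Paired RIF comparison with Xpert.** At enrolment, Xpert is described only on the Day-1 raw and decontaminated samples, so the pairing depends on Day-1 Truenat RIF results.

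A trigger worded differently for Day 1 and S4 also allows sites in several countries to apply different rules.

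**Working it through.** The point is one of consistency, and no stated figure is in dispute. The reflex rules, side by side:

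| Place in protocol | Chips run or described | What triggers the RIF chip |
|---|---|---|
| 1.2 | MTB or MTB Plus | Either chip positive |
| 8.1, Day-1 extracts | MTB and MTB Plus, both | Positive by the MTB assay (singular; MTB Plus not named) |
| 8.1, S4 | The Truenat assays (plural) | Any MTB-positive sample |
| 8.3.1 | MTB or MTB Plus | All positives on either chip |
| 10.1 | MTB or MTB Plus | All positives on either chip |

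The Day-1 row is the only one that, read literally, excludes a sample positive on MTB Plus alone. The S4 row can be read either way.

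**Size.** Inputs from section 10.2: 1,333 participants before inflation for losses, TB prevalence 20%, smear-negative share 30% of TB cases, and RIF resistance 2.8% of culture-positive cases or 12% of retreatment cases.

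- Culture-positive cases: 1,333 × 0.20 ≈ 267.
- Smear-negative: 267 × 0.30 ≈ 80, which reproduces the protocol's 80.
- Smear-positive: 267 − 80 = 187.

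The protocol does not give the share positive on MTB Plus alone. **Assumption:** 3% to 10% of smear-negative and 0% to 2% of smear-positive cases.

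- Smear-negative: 80 × 0.03 = 2.4, to 80 × 0.10 = 8.0.
- Smear-positive: 187 × 0 = 0, to 187 × 0.02 = 3.7.
- Total: 2.4 to 11.7, about 2 to 12 culture-positive participants, or 0.9% to 4.4% of 267.

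A different assumption, 2% to 15% of the smear-negative cases only, gives 80 × 0.02 = 1.6 to 80 × 0.15 = 12, much the same range.

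These counts are upper bounds at participant level. Each participant has two Day-1 extracts, and one who is MTB-positive on either of them still has a Day-1 RIF result.

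Expected RIF-resistant cases among those affected:

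- At 2.8%: 2.4 × 0.028 = 0.07, to 11.7 × 0.028 = 0.33.
- At 12%: 2.4 × 0.12 = 0.3, to 11.7 × 0.12 = 1.4.

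For scale, 267 × 0.028 ≈ 7.5 resistant cases are expected in all. The expected loss at 2.8% is 0.07/7.5 = 0.9% to 0.33/7.5 = 4.4% of them.

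**The case against.** The strongest reply is that the Day-1 sentence is loose wording and no restriction is intended. The synopsis uses the name Truenat MTB to cover both chips. The Figure 1 legend in section 1.2 names either chip and then sends MTB-positive results to the RIF chip. Section 8.1 is itself a brief summary of a workflow figure that is not reproduced here, and device instructions sit in the Manual of Procedures. Sections 8.3.1 and 10.1 make the intention plain. This stands to the extent that the text cannot show what laboratories would actually do. It does not remove the conflict: section 8.1 names the two chips separately just before the rule, and elsewhere the protocol usually uses the plural for both.

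A second reply is that S4 testing or stored eluate fills the gap. Neither clearly does. Some sites may test on Day 1 only, the S4 wording does not name MTB Plus, and no enrolment Xpert run on S4 is described. Eluate is kept for discordant results, and positivity on MTB Plus alone is not listed as a reason to run the RIF chip. Section 10.5.2 rules out imputation of missing results.

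A third reply is that the effect is small, and this stands. Section 10.2 says drug-resistant cases are more likely to be smear-positive, where the assumed MTB Plus-only share is lowest.

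**Conclusion.** The conflict is real and should be resolved; its consequence is minor to moderate. Followed as written, the Day-1 rule leaves the secondary upfront-RIF outcome, the RIF indeterminate rate and the paired RIF comparison with Xpert incomplete for extracts positive on MTB Plus alone. Under the assumed shares this is at most about 2 to 12 culture-positive participants, with 0.07 to 0.33 expected resistant cases at 2.8% and 0.3 to 1.4 at 12%. Culture-negative samples positive on MTB Plus alone would add to the untested extracts, but their number cannot be derived from the protocol.

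A reader might infer three stronger conclusions that the document does not support:

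- **That the upfront-RIF outcome cannot be measured.** All MTB-positive DNA is still reflexed, so only one subset is missing.
- **That primary endpoint 1.2 is undermined.** It concerns the accuracy of the RIF assay and remains estimable in reflexed samples. Indeterminate results are excluded from the main accuracy analysis in any case (section 5.3.5).
- **That about 13% of resistant cases would be lost.** That is 1/7.5 and presumes that one resistant case falls in the subset. The expected loss at 2.8% is 0.9% to 4.4%.

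**What to change.** Reconcile sections 8.1 (Day-1 extracts and S4), 8.3.1 and 10.1 by stating one identical trigger that matches the outcome definition. For example, in both places in section 8.1: DNA positive by the Truenat MTB assay, the MTB Plus assay or both is tested by Truenat MTB-RIF Dx. Settle this before testing starts, because no later RIF run on stored eluate is assigned to these samples.

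The cost is one sentence used in both places, a matching edit to the Manual of Procedures, and a few extra RIF chips on DNA already extracted. No specimen or visit is added, and patient care is unaffected because Truenat results are not reported to the clinic. Reporting RIF results by triggering chip would be informative but is optional; no stated objective requires it.
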